Statistical Analysis Plan

TRIAL FULL TITLE	Characterizing the humoral immune response against salivary antigens of Southeast Asian mosquito vectors of malaria and dengue with a human challenge model
TRIAL ACRONYM	SG6_SHC
INTERNAL REFERENCE NUMBER	MAL19009
TRIAL REGISTRATION	ClinicalTrials.gov Identifier: NCT04478370
PROTOCOL VERSION	2.0 dated 14 June 2020
PRINCIPAL INVESTIGATORS	[name] Shoklo Malaria Research Unit (SMRU) [name] Email: [contact]
SAP AUTHORS	[name], PhD Burnet Institute The Macfarlane Burnet Institute for Medical Research and Public Health Ltd, Melbourne, Victoria, Australia [name], PhD Centre for Epidemiology & Biostatistics, Melbourne School of Population & Global Health, University of Melbourne, Melbourne, Victoria, Australia A/[name] Biostatistics Unit, Faculty of Health, Deakin University, Melbourne, Victoria, Australia
SAP VERSION	1.2
SAP VERSION DATE	23-MAR-2023

SAP Revision History

Versio n	Key Change	Reason(s) for change	Date	Page
1.1	No change	Version prior to sample collection generation	14- JUN- 2020	
1.2	Antibody levels were log ₂ transformed to represent a two- fold change in antibody levels	To account for positively skewed antibody data and aid interpretation,	23- MAR- 2023	16
1.2	The overall effect of time will be estimated (independent of any exposure and thus representing the baseline period), with the exposure and post-exposure periods fitted as a categorical time-varying variable	Due to differences (in terms of time) between individuals transitioning from baseline, to exposure and post-exposure periods, linear splines representing these periods of fixed time were unable to be estimated.	23- MAR- 2023	16
1.2	The change in antibody levels over time, and in response to Anopheles biting exposure, will be analysed using generalised estimating equations (GEEs).	High-levels of serial correlation in antibody levels within individuals over time	23- MAR- 2023	16
1.2	Additional models will be fitted to determine the effect of concordant and discordant exposure species and antibody responses.	Concordance of the exposure species is likely to have biological relevance to the antibody outcome.	23- MAR- 2023	17
1.2	Biostatisticians were un-blinded to participant exposure species and dose	In order to perform and interpret concordant exposure species and antibody analyses.	23- MAR- 2023	11

SAP Signatures

1.1 Preface

Mosquito-borne diseases cause significant burden in populations exposed to bites of vector species across Southeast Asia (1). Malaria and dengue are endemic and pose the greatest challenges. Malaria is transmitted in rural areas and multi-drug resistant falciparum malaria has been identified as a major threat to public health in these areas (2). Consequently, considerable investment has been made to eliminate Plasmodium falciparum in the Greater Mekong Subregion, the epicenter of antimalarial drug resistance (3). In this area, the main vectors are Anopheles dirus, An. maculatus and An. minimus; several other species also contribute to the transmission (4). The efficacy of conventional vector-control measures is low (5-7) because of the ecology and biology of relevant vector species (8-10), and is particularly difficult to evaluate due to the complex transmission dynamics and low rates of disease incidence (8). Dengue viruses are transmitted by aedine mosquitoes; the main vectors are Aedes aegypti and Ae. albopictus (11). Infection can cause death and overall disease burden has drastically increased over the past decades (12). As there is no specific treatment for dengue, prevention of infection is critical to reduce morbidity and mortality. Integrated management strategies and active involvement of homeowners is necessary to control Aedes mosquitoes in urban and semi-urban environments. In rural areas where vector breeding sites also include a variety of natural water bodies (rock pools, tree holes and bamboo stumps), control is particularly challenging and personal protection with long-sleeve clothes and skin repellents is often the only option available (13).

Exposure to mosquito bites is a key parameter of the vectorial capacity equation (14) and its assessment is extremely informative for disease surveillance and trials of vector-control interventions. Exposure results from a combination of parameters including mosquito population density, aggressivity to humans, people movements and sleeping habits, and personal protection conferred by vector-control interventions (15). It is currently not possible to measure exposure accurately; mosquito biting-rate estimates are sometimes combined with data on human behaviors and vector-control to produce elusive estimates, but the cost and challenges associated with data collection are often prohibitive (15).

When blood feeding, mosquitoes inject saliva into the skin of vertebrates (16). Mosquito saliva is composed of hundreds of biologically active molecules that play essential roles in the physiology of blood feeding (17). Many saliva components have immunogenic properties and some of these antigens elicit detectable levels of antibody responses in the blood following biting exposure (18). Assessment of antibody responses directed against mosquito salivary antigens as a surrogate measure of human exposure to mosquito bites has been proposed (19). Individuals repeatedly bitten by mosquitoes develop a long-lasting broad and variable sero-reactivity to mosquito salivary antigens of the biting species (20). Serum can cross-react with salivary antigens of other mosquito species to which an individual has never been exposed to (21). As a result, it can be difficult to identify antigenic peptides that elicit transient antibody responses with adequate sensitivity and specificity. Only two *Anopheles gambiae* (gSG6-P1 and cE5) and two *Aedes* sp. (Nterm-34kDa and D7) peptides have been used for assessing exposure in large-scale epidemiological surveys and trials of vector-control (22, 23). However, critical parameters including sensitivity, specificity and half-life of the antibody responses have not

been assessed precisely: only one prospective study strived to characterize the immune responses of humans (n = 1 subject exposed to *Culex quinquefasciatus* bites) and rabbits (n = 1 subject exposed to *Ae. aegypti* bites) to mosquito salivary antigens in a challenge model of controlled exposure (18). We therefore propose to conduct a world-first clinical trial of controlled exposure to bites of uninfected laboratory-reared *Anopheles* and *Aedes* mosquitoes to identify and validate biomarkers of exposure to dengue and malaria vector bites.

The primary objective of this study is to identify and validate biomarkers of exposure to bites of *An. dirus, An. maculatus, An. minimus, Ae. aegypti* and *Ae. albopictus*. The secondary objectives are to characterize the dose-response relationship between the number of mosquito bites and antibody titers and to compare the performance of capillary blood spotted on filter paper and serum from venous blood for measuring antibody responses to mosquito salivary antigens.

This study is an exploratory, factorial randomized control trial of controlled exposure to mosquito bites with 10 arms corresponding to different species (*An. minimus, An. maculatus, An. dirus, Ae. aegypti* and *Ae. albopictus*) and numbers of bites (35 or 305 bites in total over 6 weeks). Participants will be assigned randomly to one of the 10 study arms with a 1:1 ratio using a block randomization schedule. Those with incomplete follow-up will be replaced until complete follow-up of 15 participants per arm is achieved. Serum from venous blood and capillary blood spotted on filter paper will be collected weekly from each study participant before, during and after the challenges. In addition to those described in the published literature, candidate peptides will be identified with antigen prediction algorithms using mosquito DNA sequences data (either deposited in open access databases (24) or generated using wild-caught mosquito specimens) and immunoproteomic assays carried out using protein extracts of dissected mosquito salivary glands and participants samples (20). Antibody titers will be determined with high-throughput ELISA (25) and mesoscale screening assays (26).

The Statistical Analysis Plan (SAP) for the analysis of "Characterizing antibody responses to mosquito salivary antigens of the Southeast Asian vectors of malaria and dengue with a human challenge model of controlled exposure" (ClinicalTrials.gov Identifier: NCT04478370) describes and expands upon the statistical information presented in the protocol.

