each of the study condition (Appendix B). Participants will be in the study for 112 days (Appendix C). The baseline will consist of 2 visits over 2 weeks (day 0 and day 7). In the low-exposure groups, participants will be exposed to 5 mosquito bites at weekly intervals from day 14 to day 56 (seven challenges with 5 mosquito bites/challenge over six weeks, yielding a total of 35 mosquito bites). In the high-exposure group, participants will be exposed to 5 mosquito bites on day 14 and then to 50 mosquito bites at weekly intervals from day 21 to day 56 (one challenge with 5 mosquito bites and six challenges with 50 mosquito bites/challenge over 6 weeks, yielding a total of 305 mosquito bites). The number of bites and modalities of the follow up used in this study were chosen based on previous entomological investigation conducted in this area (10, 11, 96), published reports of human challenge with mosquito bites (37, 97-99) and current knowledge on the characteristic of the humoral response against saliva antigens (31, 37, 52). Both immediate and delayed skin reactions will be recorded after day 14 and day 21 challenges, requiring additional visits at day 15 and day 22. Participants with hypersensitivity to mosquito bites will be withdrawn from the study. Both capillary and venous blood samples will be collected weekly from each study participant (Appendix D). Eighteen venous blood samples will be collected including one sample of 2 mL drawn during screening visit, 14 samples of 8.6 mL during visits 2, 3, 6, 8, 9, 10, 11, 12, 14, 15, 16, 17, 18 and 19, and 3 samples of 18.6 mL during visits 4, 13 and 20 (178.2 mL of venous blood per participant in total). Seventeen dry blood spot (DBS) samples will be made from of 300 uL of capillary blood collected during visits 2, 3, 4, 6, 8, 9, 10, 11, 12, 13, 14, 15, 16, 17, 18, 19 and 20 (5.1 mL of capillary blood per participant in total). Candidate peptides will be identified in silico using publicly available genomes sequences and B-cell epitope prediction algorithms. The kinetic of antibody titers against candidate biomarkers will be assessed by enzyme-linked immunosorbent assay (ELISA) and mesoscale screening performed with serum and DBS specimens (100). Briefly, the positivity threshold of the assay will be determined using reference sera specimens from individuals not exposed to mosquito bites, as described previously (62). The ELISA signal measured in 60 reference sera obtained from unexposed individuals (30 Thai sera obtained from the Thai Red Cross and 30 Australian sera obtained from the Burnett Intstitute) will be used to define the positivity threshold of the assay. The positivity threshold of the assay will be defined as three standard deviation (SD) above the mean optic density (Δ OD) measured for the unexposed control population. A test in the study population with a ΔOD above this cut-off will be considered positive (i.e. an immune response). The specific antibody titer of study samples will be determined by performing serial dilution experiments (101). Serial dilution will be made from study samples and the Δ OD will be determined for each dilution. The antibody titer will be defined as the highest dilution giving a positive signal. Results obtained with DBS and serum specimens will be compared in order to assess the feasibility of using DBS samples to monitor exposure to bites of mosquitoes during epidemiological studies. Serum specimens collected during visits 4 (baseline), 13 (early after the end of exposure) and 20 (post-exposure) will also be analysed with immuno-proteomic approach (2D gel electrophoresis of salivary gland protein extracts, Western blot and mass spectrometry) yielding additional information on the antigenic properties of mosquito salivary gland proteome (102).

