Two-dimensional gel electrophoresis will be performed with protein extracts made from the dissected salivary glands of 200 female adult mosquito specimens. In order to obtain a sufficient resolution, protein separation will be done on an 11 cm × 20 cm gel format. The gel proteins will be then transferred to a membrane. The membrane will be incubated with 50 mL of serum diluted 10 folds (5mL of neat serum) in order to assess the reactivity of serum IgG by Western blot (53). Reactive spots of interest will be detected by comparing the staining patterns from baseline, end of exposure and post-exposure samples. Spots of interest will be excised from the 2D gel and used to perform in gel digestion with trypsin. The protein digest will be analysed with liquid chromatography-mass spectrometry. Immunogenic proteins will be identified by searching the mass spectra with Mascot (Matrix Science Ltd.).

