2.1 Study Objectives

Primary objectives:

The primary objective of this study is to identify and validate biomarkers of exposure to bites of *An. dirus, An. maculatus, An. minimus, Ae. aegypti* and *Ae. albopictus.*

Secondary objectives:

- 1. To characterize the relationship between levels of mosquito exposure and humoral response.
- 2. To assess the feasibility of using dry blood spots made from capillary blood for the monitoring of exposure to bites of mosquito vectors of malaria and dengue.

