2.2 Endpoints

Primary endpoints:

1. The levels (continuous OD (405nm)) and seroprevalence (binary) of total IgG antibodies against *Anopheles* and *Aedes* species-specific salivary peptides mesured in human serum; including gSG6-P1, minSG6-P1, macSG6-P1, dirSG6-P1, aegN-term34kDa, albN-term34kda.

Secondary endpoints:

- 1. The levels (continuous OD (405nm)) and seroprevalence (binary) of antibodies (including different isotypes and subclasses) against *Anopheles* and *Aedes* species-specific salivary peptides; including gSG6-P1, minSG6-P1, macSG6-P1, dirSG6-P1, aegN-term34kDa, albN-term34kda.
- 2. The levels (continuous OD (405nm)) and seroprevalence (binary) of antibodies (any isotype or subclasses) against novel *Anopheles* and *Aedes* species-specific salivary peptides mesured in human serum.
- 3. The levels (continuous OD (405nm)) and seroprevalence (binary) of antibodies against *Anopheles* and *Aedes* species-specific salivary peptides mesured in human dried blood spots.

3 Study Methods

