Previous wok by Poinsignon, et al. (28) generated synthetic peptides of the An. gambiae salivary protein gSG6, and identified the peptide of the P1 region (gSG6-P1) as an immunogenic biomarker of exposure to Anopheles bites. As the homologues from the primary malaria vectors of Southeast Asia share varied sequence identity to gSG6-P1 (Table 1), we used the published sequences of the SG6 proteins (24) to synthesise species-specific Anopheles salivary antigens corresponding to the SG6-P1 region of An. gambiae (gSG6-P1), An. minimus (minSG6-P1), An. maculatus (macSG6-P1) and An. dirus (dirSG6-P1)(GenScript, New Jersey, USA). Total IgG and IgM antibodies against Anopheles species-specific SG6-P1 antigens were measure using a highthroughput ELISA protocol. Detection of total IgG and IgM against salivary antigens was performed by adapting previously published ELISA protocols (29-31), and optimising them into a high-throughput protocol outlined below. Spectraplates (Perkin Elmer) were coated with 0.5µg/mL of Anopheles salivary peptides (Genscript) resuspended in autoclaved MilliQ water and diluted in PBS, and incubated for 3 hours at 37°C. Plates were washed and blocked for one hour at 37°C with Blocking Buffer (Pierce, Thermo Scientific USA). After a subsequent wash step, sera were added at a desired concentrations (diluted in 10% Blocking Buffer with PBS) and incubated overnight at 4°C. Following sera incubation, plates were washed and secondary antibody added. To detect human IgG and IgM, HRP-conjugated goat anti-human IgG (Millipore) and HRP-conjugated goat anti-human IgM (Millipore) was used at a 1:500 dilution. Plates were incubated at 37°C for 1.5 hours and then washed. ABTS (2,2'-azino-bis(3-ethylbenzothiazoline-6sulfonic acid)) substrate was added to each well, covered and left to develop at room temperature, then stopped with 1% sodium dodecyl sulphate (SDS), and the OD was read in a spectrophotometer at 405nm.

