9.1 Effect of mosquito biting exposure on antibody level and seropositivity

Measurement of mosquito species-specific antibodies will be using high-throughput ELISA are described in Table 3:

Assay	Visits	Outcomes
High-throughput ELISA	Visits 2-	Total Anti-IgG levels and seropositivity against:
	20	gSG6-P1
		minSG6-P1
		macSG6-P1
		dirSG6-P1
		aegNterm34kDa

Table 3 Overview of assays

Assay	Visits	Outcomes
		albNterm34kDa
High-throughput ELISA	Visits 2-	Total Anti-IgM levels and seropositivity against:
	20	gSG6-P1
		minSG6-P1
		macSG6-P1
		dirSG6-P1
		aegNterm34kDa
		albNterm34kDa
High-throughput ELISA	Visits 2-	Total antibody (including any isotype or subclass)
	20	levels and seropositivity against novel candidate
		Anopheles and Aedes species-specific antigens

Antibody markers will be summarised at each scheduled time point, including changes from baseline. Values will be presented visually with dotplots at each time point and spaghetti plots to visualise within-participant changes from baseline.

The change in antibody levels (as a continuous outcome and binary response) over time will be analysed using generalised linear mixed-effects models. Optical density measurements (*i.e.* antibody levels) will be analysed using a Gaussian distribution family and identity link function (*i.e.* a linear mixed-effects model) and binary responder status will be analysed using a Binomial distribution family and a logit link function (*i.e.* a logistic mixed-effects model). Linear splines will be fitted to represent the baseline (visits 2-3), exposure to mosquito bites (visits 4-12) and post exposure (visits 13-20) periods to model the boosting and decay of antibody responses. Mixed-effects models will include a random effect (*i.e.* intercept) for participant to allow random variations of immune responses in individuals. Estimates from the linear mixed-effects models will be used to calculate the half-lives of each antibody measure.

Amendment to SAP 23/03/2023

To account for positively skewed antibody data and aid interpretation, antibody levels were log₂ transformed to represent a two-fold change in antibody levels.

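### Antigens found by blotting participants' own sera would be tested for a bite response in the same participants, so those results are discovery and not validation

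*SAP*

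**What the plan says.** **Where candidates come from.** SAP 1.1 gives three routes. Some peptides are already published. For others, "candidate peptides will be identified with antigen prediction algorithms using mosquito DNA sequences data". The third route is "immunoproteomic assays carried out using protein extracts of dissected mosquito salivary glands and participants samples". Protocol 5 names only the computational route ("Candidate peptides will be identified in silico using publicly available genomes sequences and B-cell epitope prediction algorithms") and treats the blots as extra information on antigenic properties. The SG6-P1 peptides come from published sequences (SAP 3.1: "we used the published sequences of the SG6 proteins (24) to synthesise species-specific").

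**How the third route selects.** Protocol 7.7 blots separate 5 mL serum aliquots from visits 4, 13 and 20, using individual rather than pooled sera. The rule is: "Reactive spots of interest will be detected by comparing the staining patterns from baseline, end of exposure and post-exposure samples". The number of participants to be blotted is not stated.

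**How novel peptides are tested.** Secondary endpoint 2 in SAP 2.2 covers levels and seroprevalence "of antibodies (any isotype or subclasses) against novel" salivary peptides. The third row of Table 3 in SAP 9.1 measures "levels and seropositivity against novel candidate" antigens by ELISA over visits 2-20. The analysis set is everyone randomised with at least one valid measurement (SAP 7.2.1). Multiplicity is not adjusted for (SAP 7.5), and SAP 10 rules out further analyses. Neither document mentions a hold-out sample, cross-validation or an independent cohort.

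**What is claimed.** SAP 2.1: "The primary objective of this study is to identify and validate biomarkers of exposure to bites of" the five species. The primary objective in Protocol 4 is only to identify, although Protocol 3.5 also speaks of validating markers.

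**The concern.** If an antigen is chosen because reactivity rose after biting in certain people, a later estimate of the rise in those people contains the chance part of what got it chosen. Changing the assay from blot to ELISA does not remove this, because both read the same person's antibody change. Change from baseline, seropositivity and half-life can all look better than they would in new people.

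The stake is what may be concluded. Protocol 3.5 foresees use of these markers in surveillance and in vector-control trials. A marker put forward as validated should have been assessed in people who played no part in choosing it.

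**Working it through.** **1. Design figures.** 5 species x 2 doses x 15 = 150, and 15 blocks x 10 = 150, as in Protocol 7.4. That gives 2 x 15 = 30 participants per species. The documents give no standard deviation, effect size or antigen count, so the size of the problem has to be explored under assumptions.

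**2. Overlap of samples.** ELISA sera are drawn at visits 2, 3, 4, 6 and 8-20, which is 17 draws. Blots use 3 of those visits, so 17 - 3 = 14 draws are never blotted. The people overlap; most of the draws do not.

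**3. Simplest test: a paired before-after ELISA change.** Assume that no antigen is truly boosted, that one species has 30 participants, and that the spots with the largest blot rise are selected. A false rise is the upper tail of a two-sided 5% test, nominally 2.5%.

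Top 3 chosen on the visit 4 to visit 13 change, all 30 blotted:

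| Spots | Blot-ELISA correlation | False rise per selected peptide |
|---|---|---|
| 20 | 0.3 | 6% |
| 50 | 0.5 | 13% |
| 100 | 0.7 | 28% |
| 100 | 0.9 | 49% |

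Top 5 chosen, 20-200 spots, correlation 0.3-0.8, tested in all 30:

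| Participants blotted | False rise | Upward bias in mean change |
|---|---|---|
| 30 of 30 | 5-39% | 0.07-0.33 SD |
| 15 of 30 | 4-21% | 0.05-0.24 SD |
| 5 of 30 | 3-8% | 0.03-0.13 SD |

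When the test used only participants who had not been blotted, the false-rise rate was 2.1-3.1% and the bias was within 0.01 SD.

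**4. The model the SAP plans.** SAP 9.1 (amended) fits a GEE with autoregressive correlation, a time term and exposure and post-exposure periods. SAP 8.2 assigns visits 4-12 to exposure. Assume all 30 blotted, top 3 chosen, the four settings of the first table, and stationary serially correlated noise (weekly correlation 0.7-0.95, with 0-30% independent noise):

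- Visit 4 coded as exposure, linear time term: about 0.3-3% false rises. With the period-by-time interactions that SAP 9.1 also plans, up to about 6.5%.
- Visit 4 coded as baseline, time term kept: roughly 3-10%, and up to 16% in one set of runs.
- Visit 4 coded as baseline, no time term: up to about 32%.
- Raw change from visits 2-3 to the post-exposure period: 4-26%.

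The first case is near nominal because a chance-low visit 4 pulls the exposure-period estimate down and the time term absorbs part of any drift. But the visit 4 sample is taken before the bites (Protocol Appendix C, note c), and Protocol 7.7 calls it baseline for the blots. The protection therefore depends on a coding that places a pre-bite sample in the exposure period.

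**5. Cost of separating the data.** If 10 of 30 per species are blotted, 20 remain. The standard error ratio is sqrt(30/20) = 1.22. By the normal approximation, power for a true 0.5 SD change is Phi(0.5 x sqrt(n) - 1.96), which is 78% at n = 30 and 61% at n = 20.

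**The case against.** Several objections stand.

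- **Scope.** A reader might infer that every novel antigen, or even the primary endpoint, is circular. The documents do not support that. Only one of three routes uses participants' sera, and none of the six peptides named in SAP 2.2 is tied to them.
- **Inference.** Neither document says outright that blot-derived peptides go on to ELISA in the same people. It follows from SAP 1.1, which lists them as candidates and then says titers will be measured by ELISA, read with Table 3. That is the natural reading, but it is a reading.
- **Size.** A reader might infer false-positive rates near one half in the planned analysis. Those belong to a paired visit 4 to visit 13 test that the SAP does not specify, with everyone blotted. Spots are also to be chosen by comparing staining patterns, not by a formal ranking.
- **Tone of the plan.** SAP 1.1 calls the trial exploratory, novel peptides are secondary, SAP 8 says comparative analyses will be described qualitatively, and the positivity cut-off comes from Melbourne controls (SAP 3.1). It is speculation that a chance antigen would be published as validated.

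What does not answer the point: an exploratory label covers discovery but not the word validate in SAP 2.1. Unblotted participants would be a clean test set, but the SAP neither identifies them nor restricts testing to them. A near-nominal false-rise rate for one coding of one model does not protect the change-from-baseline summaries that SAP 9.1 also plans.

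**Conclusion.** The point holds for immuno-proteomic antigens only. They are selected on a before-to-after-bite change in participants' sera and, on the natural reading, assessed for the same kind of change in the same participants with no separation. Their change, seropositivity and half-life estimates can be optimistic and cannot serve as validation.

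The size cannot be fixed from the documents. Under the assumed values it runs from about nominal (the planned GEE with visit 4 as exposure and a time term), through roughly 3-10% (visit 4 as baseline) and up to about 30% (time term also dropped), to about 50% (raw paired visit 4 to visit 13 change with all 30 per species blotted). It shrinks as fewer participants are blotted. This is a cheap improvement that limits what may be concluded; it does not undermine the primary endpoint.

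**What to change.** In SAP 2.2 and 9.1:

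1. Record the origin of each novel peptide: literature, sequence prediction or immuno-proteomics.
2. List the participants whose sera were blotted.
3. Estimate the performance of blot-derived peptides only in participants who were not blotted, or by cross-fitting.
4. If everyone was blotted and cross-fitting is not done, report these peptides as discovery only, without confirmatory p-values and without calling them validated.

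All other peptides keep all 150 participants.

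The cost is SAP wording plus wider intervals on this route alone: a standard error about 22% larger if 10 of 30 per species are blotted, with the power loss shown above. Limiting the number blotted also costs discovery yield. An antigen recognised by 10% of people (an assumed figure) shows in at least one of 10 blotted with probability 1 - 0.9^10 = 65%, against 1 - 0.9^30 = 96% for 30. How many to blot is therefore a trade-off for the investigators, and cross-fitting is the alternative if they want to blot everyone.
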